8.2.3.3. Subgroup Analysis

Number of vaccinees experiencing at least one adverse reaction and its proportion are to be calculated by subgroups as defined in [Section 5.4](#) (excluding subjects ineligible for vaccination). To assess the association between vaccinee characteristics and occurrence of adverse reactions, risk ratio and its 95% confidence interval are to be calculated as described in [Section 8.1.3](#).

To evaluate the safety in specific populations of vaccinees in detail, analyses are to be performed in the following subgroups.

- **Vaccinees with hepatic dysfunction, renal dysfunction and simultaneous vaccination with other vaccine**

Number of vaccinees experiencing adverse reactions and its proportion are to be calculated by SOC and PT in each subgroup.

- **Vaccinees with immunocompromised complication**

Number of vaccinees experiencing adverse reactions, local and systemic reactions and adverse events with its proportion are to be calculated by SOC and PT.

- **Vaccinees with prior vaccination of polyvalent pneumococcal polysaccharide vaccines**

Number of vaccinees experiencing adverse reactions, local and systemic reactions and adverse events with its proportion are to be calculated by SOC and PT by prior vaccination of polyvalent pneumococcal polysaccharide vaccines [1 year ago from the day before Prevenar13 vaccination, 1-5 years ago, more than 5 year ago, unknown date].

- **Vaccinees with immunocompromised complication and prior vaccination of polyvalent pneumococcal polysaccharide vaccines**

Number of vaccinees experiencing adverse reactions, local and systemic reactions with its proportion are to be calculated by SOC and PT by prior vaccination of polyvalent pneumococcal polysaccharide vaccines [1 year ago from the day before Prevenar13 vaccination, 1-5 years ago, more than 5 year ago, unknown date].

- **Subjects ineligible for vaccination**

Reports described below are to be prepared for subjects ineligible for vaccination (See [Section 5.4](#)) and used as a reference for reporting safety information of these subjects. If there are less than 10 subjects ineligible for vaccination, however, safety information of these subjects are to be reported with a listing of vaccinees and other forms, and reports described below are not to be prepared.

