Number of subjects ineligible for vaccination as described in the package insert and its proportion are to be calculated. In addition, number of the following subjects ineligible for vaccination as described in the package insert which would be identifiable in this survey is to be calculated:

- Subjects with apparent pyrexia;
- Subjects with documented serious acute disease.

Number of subjects ineligible for vaccination with at least one adverse reaction is to be calculated.

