9. LISTING

The following listings are to be prepared:

- Listing of vaccines;
- Listing of vaccinees (safety analysis population);
- Listing of vaccinees who experienced adverse events;
- Listing of vaccinees who experienced adverse reactions;
- Listing of vaccinees excluded from safety analysis population who experienced adverse reactions;
- Listing of vaccinees experiencing serious adverse reactions;
- Listing of vaccinees experiencing serious adverse events;
- Listing of vaccinees with hepatic dysfunction who experienced adverse reactions;
- Listing of vaccinees with renal dysfunction who experienced adverse reactions;
- Listing of vaccinees with immunocompromised complication who experienced adverse reactions;
- Listing of vaccinees with prior vaccination of polyvalent pneumococcal polysaccharide vaccines who experienced adverse reactions;

- Listing of vaccinees with immunocompromised complication and prior vaccination of polyvalent pneumococcal polysaccharide vaccines who experienced adverse reactions.

Additionally, the following listings are to be included in the attached forms of periodic safety reports:

[figure not shown]
- Attached form 3 (Listing of occurrence of ADR/Infection case report);
- Attached form 2 (Listing of occurrence of ADR/Infection);
- Attached form 10 (Attached form 2-2) (Listing of occurrence of serious adverse events).

If there are at least 10 subjects ineligible for vaccination (See [Section 5.4](#)), listings including the following information are to be prepared:

- Case number;
- Criteria for subjects ineligible for vaccination;
- Name of institution;
- Date of vaccination;
- Completion/discontinuation of observation and reason for discontinuation if applicable;
- Presence or absence of adverse reactions;
- Details of each adverse reaction: name of adverse reaction (SOC and PT), date and timing of onset (calculated with day of vaccination as Day 0), date and timing of outcome (calculated with day of vaccination as Day 0), severity, corrective treatment, seriousness and outcome.

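### With 10 or more ineligible vaccinees, their dedicated safety count and listing show only attributed adverse reactions, so events judged due to the existing illness do not appear there

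*SAP*

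**What the plan says.** SAP 5.4 defines the ineligible subgroup through a separate extraction procedure and gives it no reference category. SAP 8.2.3.3 names two kinds of ineligibility that the survey can identify: "Subjects with apparent pyrexia" and "Subjects with documented serious acute disease". It describes the planned reports as reference material for reporting these subjects' safety.

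The outputs depend on the size of the group:

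- **Ten or more.** SAP 8.2.3.3 gives the number and proportion ineligible, the number in each of the two categories, and one safety result: "Number of subjects ineligible for vaccination with at least one adverse reaction is to be calculated". SAP Section 9 adds a listing on the same condition ("If there are at least 10 subjects ineligible for vaccination"). Its safety items are "Presence or absence of adverse reactions" and "Details of each adverse reaction: name of adverse reaction (SOC and PT), date and timing of onset", followed by outcome, severity, treatment and seriousness of those reactions.
- **Fewer than ten.** The dedicated reports are dropped. The rule, quoted up to its last word, is: "safety information of these subjects are to be reported with a listing of vaccinees and other forms, and reports described below are not to be". That fallback is not limited to adverse reactions.

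SAP 6.1 separates an adverse reaction, which needs attribution by investigator or sponsor, from an adverse event, which does not. For vaccinees with an immunocompromised complication, SAP 8.2.3.3 asks for more: "Number of vaccinees experiencing adverse reactions, local and systemic reactions and adverse events with its proportion are to be calculated by SOC and PT". The subgroup with prior polysaccharide vaccination gets the same three types of result.

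**The concern.** A count limited to attributed events is least informative in people who were febrile or acutely ill when vaccinated. If such a person worsens, is admitted or dies, the existing illness is an obvious explanation, and the event may be attributed to it by both investigator and sponsor. It then enters neither the subgroup's count nor its listing.

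The information exists. Protocol 9.4.1 gives worsening of the primary disease as an example of an adverse event, and Protocol 9.1 requires all serious and non-serious adverse events in the CRF. The survey's second objective (SAP 2.2) is the occurrence of adverse events, not only of reactions. Protocol 7.9 acknowledges that there is no control group, so an all-cause count beside the attributed one would be a simple check on how much the subgroup result depends on causality judgements.

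**Working it through.** The point is textual and contests no figure in the plan. It is checked first by tracing one event through the outputs, then by illustrating size.

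**1. Tracing an event.** Suppose an ineligible vaccinee in the safety analysis population has a serious worsening that neither investigator nor sponsor attributes to the vaccine.

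| Output | Does the event appear? |
|---|---|
| SAP 8.2.3.3, ineligible-subject count (10 or more) | No: adverse reactions only |
| SAP 9, ineligible-subject listing (10 or more) | No: presence and details of adverse reactions only |
| SAP 8.2.3.3, general subgroup table | No: leaves out ineligible subjects and uses adverse reactions |
| SAP 8.2.3.2, adverse event tables by SOC and PT | Yes, but not separated by ineligibility |
| SAP 9, listings of vaccinees with adverse events and serious adverse events | Yes, but no ineligibility flag is specified |

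The ineligible-subject listing does carry the case number and any reason for discontinuation. A reader could therefore match cases by hand, and an early end of observation would show. The event itself would not.

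**2. Is the report likely to exist?** The threshold is 10/600 = 1.67% of planned registrations. The documents do not give the proportion ineligible. For an assumed proportion q, P(at least 10) is the upper tail of Binomial(600, q):

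| Assumed q | P(at least 10 of 600) |
|---|---|
| 0.5% | 0.1% |
| 1% | 8.3% |
| 1.5% | 41% |
| 2% | 76% |
| 3% | 98.6% |

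**3. How many vaccinees would be missing?** The earlier Japanese studies give investigator-reported adverse reaction rates of 13/333 = 3.9% and 9/136 = 6.6% (Protocol 7.5.2, SAP 2.1). Assume n = 20 ineligible vaccinees and an any-event risk a of 10% to 30%. With reaction rate r, the expected number with only unattributed events is n(a − r), and the chance of at least one is 1 − (1 − (a − r))^n.

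- Lowest: 20 × (0.10 − 0.066) = 0.68; 1 − 0.966^20 = 50%.
- Highest: 20 × (0.30 − 0.039) = 5.22; 1 − 0.739^20 = 99.8%.
- Expected with an adverse reaction: 20 × 0.039 = 0.8 to 20 × 0.066 = 1.3. Expected with any event: 2 to 6.

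**4. Chance that the planned count is zero.** Let p be the any-event risk and s the share of affected vaccinees whose event is attributed. Then P(zero) is (1 − ps)^n for reactions and (1 − p)^n for all events. With assumed n = 15, p = 20%, s = 25%: 0.95^15 = 46% against 0.8^15 = 4%. Over n = 10 to 20, p = 10% to 30% and s = 10% to 50%, the reaction count is zero with probability 4% (0.85^20) to 90% (0.99^10). The all-event count is zero with probability below 1% (0.7^20) to 35% (0.9^10).

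**5. A limit on step 4.** This survey uses a diary to Day 13 (Protocol 7.2.6), and diary-reported local reactions in the earlier studies were 55.8% and 63.6%. If such reactions are recorded as adverse reactions here, the count could be well above zero: 15 × 0.558 = 8.4 at the lower rate. A count made up of local reactions would still say nothing about unattributed deterioration, so step 1 does not depend on step 4.

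**The case against.** The strongest reply is that the plan is following its own design. Protocol 7.7 makes the incidence of adverse reactions the primary endpoint and examines background factors on it. The hepatic, renal and simultaneous-vaccination subgroups, and the combined immunocompromised and prior-vaccine subgroup, are also reaction-only. The two subgroups that receive adverse events correspond to named safety specifications in Protocol 6.1, and ineligible vaccinees do not. This stands as an explanation, and it rules out any claim that this subgroup was singled out. It does not make the restriction suitable for a group identified by acute illness at vaccination, and the addition leaves the primary endpoint alone.

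A reader might infer that these events are lost. The documents do not support that: they enter the whole-population tables and listings, and every serious adverse event is reported to the sponsor within 24 hours whatever its cause (Protocol 9.1). SAP Section 9 gives only titles for the general listings, so an ineligibility column is unspecified rather than ruled out.

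A reader might also infer that a low count would be used as reassurance about vaccinating such people. No passage says so. The SAP calls the reports a reference, sets no decision rule (4.2) and allows further analyses as needed (8.2.3.4), although those are optional and reported selectively.

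Finally, full SOC and PT tables of all events would be sparse in a small group and would largely describe the underlying illness. That is accepted.

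**Conclusion.** The point holds within a narrow scope. When at least 10 vaccinees are ineligible, the count and listing prepared for them exclude any event that neither investigator nor sponsor attributes to the vaccine. Such events can be found only by matching cases to the general listings. Below 10 the issue does not arise in this form.

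The exclusion rests on the text alone. Its size does not: group size, any-event risk and attributed share are all assumed, and the 3.9% and 6.6% reaction rates come from study populations rather than from people vaccinated while ill. The illustrative 0.7 to 5.2 vaccinees missing out of 20 is therefore a range of possibilities, not an estimate. No endpoint, sample size or error rate is affected. This is a worthwhile, inexpensive improvement to one conditional report.

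**What to change.** In SAP 8.2.3.3, under subjects ineligible for vaccination, add the number and proportion with at least one adverse event and with at least one serious adverse event, both regardless of causality, beside the planned adverse reaction count. In the SAP Section 9 listing for this group, list all adverse events with seriousness and a causality column. SOC and PT tables are optional given the likely group size.

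The cost is a few lines of SAP wording, two added counts with proportions, and a wider listing from data already in the CRF. The small downside is that some listed events will reflect the underlying illness, which the causality column makes visible. This changes reporting only and proposes no clinical rule.

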8.2.3.4. Exploratory Analysis

Additional analysis may be performed as necessary. Results from exploratory analysis will be reported only if they provide important interpretation.

8.2.4. Efficacy Analysis

No efficacy analysis is to be performed in this survey.

9. LISTING

The following listings are to be prepared:

- Listing of vaccines;
- Listing of vaccinees (safety analysis population);
- Listing of vaccinees who experienced adverse events;
- Listing of vaccinees who experienced adverse reactions;
- Listing of vaccinees excluded from safety analysis population who experienced adverse reactions;
- Listing of vaccinees experiencing serious adverse reactions;
- Listing of vaccinees experiencing serious adverse events;
- Listing of vaccinees with hepatic dysfunction who experienced adverse reactions;
- Listing of vaccinees with renal dysfunction who experienced adverse reactions;
- Listing of vaccinees with immunocompromised complication who experienced adverse reactions;
- Listing of vaccinees with prior vaccination of polyvalent pneumococcal polysaccharide vaccines who experienced adverse reactions;

- Listing of vaccinees with immunocompromised complication and prior vaccination of polyvalent pneumococcal polysaccharide vaccines who experienced adverse reactions.

Additionally, the following listings are to be included in the attached forms of periodic safety reports:

[figure not shown]
- Attached form 3 (Listing of occurrence of ADR/Infection case report);
- Attached form 2 (Listing of occurrence of ADR/Infection);
- Attached form 10 (Attached form 2-2) (Listing of occurrence of serious adverse events).

If there are at least 10 subjects ineligible for vaccination (See [Section 5.4](#)), listings including the following information are to be prepared:

- Case number;
- Criteria for subjects ineligible for vaccination;
- Name of institution;
- Date of vaccination;
- Completion/discontinuation of observation and reason for discontinuation if applicable;
- Presence or absence of adverse reactions;
- Details of each adverse reaction: name of adverse reaction (SOC and PT), date and timing of onset (calculated with day of vaccination as Day 0), date and timing of outcome (calculated with day of vaccination as Day 0), severity, corrective treatment, seriousness and outcome.

10. APPENDIX

10.1. Appendix 1: Example of a Chart of Risk Ratio of Incidence of Adverse Reactions by Subgroups

10.2. Appendix 2: Definition of Events

10.2.1. Local Reaction

Local reaction is defined as an adverse reaction coded as Primary High Level Term of “vaccination site reactions”.

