6.1. Safety Specifications

- 1) Safety in persons with immunocompromised state
- 2) Safety of concurrent vaccination with other vaccines
- 3) Safety in the elderly (adults aged 65 years or older) who received multiple vaccinations with Prevenar 13
- 4) Safety of Prevenar 13 in the elderly (adults aged 65 years or older) with a history of immunization with polyvalent pneumococcal capsular polysaccharide vaccines

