7.3.7 AEs

The investigator should record the below mentioned information after checking the occurrence of AEs during the AE collection period. Particularly, the vaccinees should be explained to notify local and systemic reactions, if occurred, to the investigator. If AEs are identified, the investigator should take appropriate therapeutic actions, immediately inform the sponsor, and monitor the outcome and course until symptoms resolve, as a rule. If the sponsor determines it necessary in vaccinees with serious adverse reactions, adverse reactions such as local and systemic reactions in the investigation, adverse reactions not specified in the package insert, etc., a detailed investigation should be separately performed.

- (1) Whether or not AEs occurred
- (2) AE term
- (3) Date of onset
- (4) Severity
- (5) Therapeutic action taken or not taken (if taken, its detail)
- (6) Seriousness
- (7) Outcome
- (8) Causal relationship with Prevenar 13

[Assessment of severity]

The investigator should record the maximum severity during the period from the onset of the AE to the confirmation of its outcome using mild, moderate, or severe (for pyrexia, mild, moderate, severe or possibly life-threatening). The severity will be defined as follows (Table 3):

Table 3 Definition of severity

	Absent	Mild	Moderate	Severity	Possibly life-threatening
Injection site erythema and swelling	< 2.5 cm	≥ 2.5 cm, ≤ 5.0 cm	> 5.0 cm, ≤ 10.0 cm	> 10.0 cm	-
Pyrexia	< 37.5°C	≥ 37.5°C, ≤ 38.4°C	≥ 38.5°C, ≤ 38.9°C	≥ 39.0°C, ≤ 40.0°C	> 40.0°C
Other AEs	-	Not interfering with the normal function of the vaccinee	Interfering with the normal function of the vaccinee to some degree	Significantly interfering with the normal function of the vaccinee	-

[If an AE of pyrexia occurs, the following information should be additionally entered:]

- (1) Date of measurement
- (2) Body temperature

Be sure to record the maximum body temperature during the period from the onset of pyrexia to its resolution.

[In the case of AEs related to laboratory tests, etc. and abnormal changes in test values, the following should be additionally entered:]

- (1) Name of test
- (2) Site reference value
- (3) Unit
- (4) Date of measurement
- (5) Results

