7.5.2 Rationale

In the age group of 65 years or older in a clinical study, B1851088 (noninferiority study) involving elderly subjects (adults aged 65 years or older) without history of immunization with pneumococcal vaccines and a clinical study, 6115A1-3004 (open-label study) involving

adults aged 50 years or older conducted in Japan, the incidence of local reactions reported by the subjects using an electronic diary during 14 days after vaccination with Prevenar 13 was 55.8% and 63.6%, respectively, and the incidence of systemic reactions was 37.9% and 52.6%, respectively. In the two studies, the incidence of AEs (adverse reactions) related to Prevenar 13 reported by the investigators during approximately one month after vaccination with Prevenar 13 was 3.9% (13/333) and 6.6% (9/136), respectively. The results of comparison between Japanese and overseas clinical study data revealed no new risk factor requiring attention in the Japanese subjects aged 65 years or older. In the Japanese clinical studies, 518 elderly subjects aged 65 years or older (B1851088, n = 382; and 6115A1-3004, n = 136) received Prevenar 13, and 469 subjects included in the safety set (B1851088, n = 333; and 6115A1-3004, n = 136) were evaluated for safety. Consequently, for the safety of Prevenar 13 under actual use conditions after marketing, a planned sample size of the investigation was set to 600 persons to collect and examine safety information from a subject scale equivalent to those of the Japanese clinical studies.

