For the vaccinees whose CRFs collected, a listing of adverse reactions in the vaccinees excluded from safety analysis population is to be prepared. Additionally, number of vaccinees experiencing adverse reactions is to be calculated by inclusion of/exclusion from safety analysis population by SOC and PT.

- **Local reaction**

Number of vaccinees experiencing local reactions and its proportion are to be calculated by SOC and PT. See [Section 10.2.1](#) for definition of local reaction.

- **Systemic reaction**

Number of vaccinees experiencing systemic reactions and its proportion are to be calculated by SOC and PT. See [Section 10.2.2](#) for definition of systemic reaction.

- **Pyrexia**

Number of vaccinees experiencing pyrexia and its proportion are to be calculated by presence or absence of immunocompromised complication and simultaneous vaccination with other vaccine. See [Section 10.2.3](#) for definition of pyrexia.

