10.2.3. Pyrexia

Pyrexia is defined as an adverse reaction coded as PT of either “hyperthermia”, “hyperpyrexia”, “pyrexia”, or “body temperature increased”.

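### SAP 10.2.1 admits local reactions through one vaccination-site High Level Term, while the protocol speaks of injection-site events and nothing in either document ensures that the two meet

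*SAP*

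**What the plan says.** The SAP fixes the local reaction endpoint in Appendix 2, section 10.2.1: "Local reaction is defined as an adverse reaction coded as Primary High Level Term of “vaccination site reactions". No other High Level Term or PT is admitted.

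The definition feeds two sets of tables:

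- SAP 8.2.3.1, under Local reaction, refers to 10.2.1 and plans the overall table: "Number of vaccinees experiencing local reactions and its proportion are to be calculated by SOC and PT".
- SAP 8.2.3.3 plans, for vaccinees with an immunocompromised complication and for those with prior polysaccharide vaccination: "Number of vaccinees experiencing adverse reactions, local and systemic reactions and adverse events with its proportion are to be calculated by SOC and PT". Local reactions are also tabulated for vaccinees with both features.

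On the collection side, Protocol 7.3.7 has the investigator enter an AE term and grade its severity from Table 3. The local row of that table reads "Injection site erythema and swelling".

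**The concern.** The selection rule works on coded terms and uses one site word. The protocol, which investigators work from, uses another. Neither document names the coding dictionary or its version, gives a coding convention, or says that an event reported as an injection-site event will be coded to a vaccination-site term. The separate procedures that the SAP cites (sections 5.1 and 5.4) cover analysis-set handling, hepatic and renal dysfunction, the immunocompromised definition and subjects ineligible for vaccination. None is described as covering term coding.

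If some local reactions were coded to injection-site terms outside the named High Level Term, a programmer following 10.2.1 would leave them out. Two of the subgroups concerned match safety specifications in Protocol 6.1: item 1, "Safety in persons with immunocompromised state", and item 4, on prior polysaccharide vaccination. In a safety survey, an omission of this kind errs in the reassuring direction.

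**Working it through.** **Direction.** Let V be the vaccinees with at least one adverse reaction in the vaccination-site High Level Term. Let U be those with at least one adverse reaction in that group or under an injection-site reaction PT. V is a subset of U, so V/n ≤ U/n. The present rule can equal the wider count or fall below it, but cannot exceed it. A vaccinee is lost from the total only if all of that person's local reactions are coded outside the High Level Term.

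**What other planned tables recover.** SAP 8.2.3.1 tabulates all adverse reactions by SOC and PT, and 8.2.3.3 does so in the subgroups named above. An injection-site PT would appear there. These rows do not give a local total, because a vaccinee with both erythema and swelling sits in two of them. The number of distinct vaccinees lies between the largest row and the sum of the rows, and the tables do not say where.

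**Inputs for size.**

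- Planned registration: 600 (Protocol 7.5.1).
- Local reactions reported by diary in the two Japanese studies, "during 14 days after vaccination with Prevenar 13 was 55.8% and 63.6%, respectively" (Protocol 7.5.2).
- Investigator-reported adverse reactions of any kind in the same studies: 13/333 and 9/136 (Protocol 7.5.2). Recomputed, these are 3.9% and 6.6%, as stated.

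Two assumptions are needed: that all 600 enter the safety analysis set, and that one or other set of rates carries over to this survey.

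**One vaccinee.** 1/600 = 0.17 percentage points.

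**Vaccinees who depend on the rule, 600 × p.**

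| Assumed rate p | 600 × p | Fall in reported rate per 1% coded wholly outside the term |
|---|---|---|
| Diary, 55.8% | 334.8, about 335 | 3.35/600 = 0.56 points |
| Diary, 63.6% | 381.6, about 382 | 3.82/600 = 0.64 points |
| Investigator, 13/333 | 23.4, about 23 | 0.23/600 = 0.04 points |
| Investigator, 9/136 | 39.7, about 40 | 0.40/600 = 0.07 points |

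The two investigator rows are upper limits, because those rates cover adverse reactions of every kind and not only local ones.

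**Range.** With f the share of these vaccinees coded wholly outside the term, the reported rate is p × (1 − f). The loss runs from zero at f = 0 to the whole of p at f = 1. The documents do not locate f, so the table gives conversion factors and not an estimate. They also give no subgroup sizes, so no subgroup figure can be worked out.

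**The case against.** The strongest reply is that no defect has been shown. The rule loses cases only if the dictionary places injection-site terms outside the named group and coders used those terms in a survey of a vaccine. The documents establish neither. Table 3 is a severity grid and does not prescribe the coded term, so its row label and a dictionary group need not share wording. The two documents often render the same content in different English (concurrent and simultaneous vaccination, for instance), so one phrase is weak evidence about coding practice. Data management is outsourced (Protocol section 12), and a convention may exist elsewhere. All of this stands, and it limits the point to an unspecified link.

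Two stronger readings are tempting:

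- A reader might infer that the local rate will be under-reported, or that the protocol and SAP contradict each other. The documents support neither, for the reasons just given.
- A reader might set 10.2.1 against 10.2.3, which accepts four PTs for pyrexia, and conclude that 10.2.1 is the narrower definition. That compares a grouping term with individual PTs. The High Level Term may itself hold several PTs, and the planned layout by PT suggests that it does.

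It is also fair to say that no data would be lost. The all-adverse-reaction tables would reveal an omitted PT, and SAP section 9 plans vaccinee-level listings, among them "Listing of vaccinees with immunocompromised complication who experienced adverse reactions", from which a recount could be made by hand. That reduces the consequence. It does not put the right total into the planned local reaction tables.

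A last objection is that simply adding injection-site terms would be vague and would leave other site wording uncovered. That is met by listing the exact terms.

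**Conclusion.** The point holds as a gap in specification. The local reaction total depends on one site term, and nothing in the documents ensures that events described in the protocol's own words reach it. Any error lowers the reported local rate and is confined to the local reaction tables in SAP 8.2.3.1 and 8.2.3.3. Its size is unknown and may be zero. The figures above show only how much would turn on the rule, and they rest on carrying the earlier studies' rates over to this survey.

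The primary endpoint, the incidence of any adverse reaction (Protocol 7.7), does not use the definition, and the sample size does not rest on it. The survey sets no statistical decision rule (SAP 4.2), so no formal conclusion is at risk. This is a low-priority safeguard that costs almost nothing.

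**What to change.** In SAP 10.2.1, define a local reaction as an adverse reaction whose primary High Level Term is the vaccination-site reaction group, or whose PT is an injection-site reaction term. List the High Level Terms or PTs used, so that two programmers would select the same records. Keep the requirement that the event is an adverse reaction under SAP 6.1, and count each vaccinee once in the local total. Do not add a condition on anatomical site, because the AE items in Protocol 7.3.7 do not record one.

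The cost is a revised definition with a short term list and a wider selection in the local reaction programs. No new data are needed, and neither the sample size nor the primary endpoint changes. If every local reaction is already coded to the vaccination-site group, the tables come out the same. Otherwise the local rate can only rise.
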